5.1.8.2. HBV Diagnosis and Infection Dates

If the reported date is partially missing, the following imputation rules will be applied:

- the 15th of the month, if only the day is missing.
- the 30th of June, if only the year is available.
- No imputation if completely missing.

5.1.8.3. Concomitant Medication Dates

In case of partially missing concomitant medication start/end dates, the following imputation rules will be applied:

- the 15th of the month, if only the day is missing.
- the 30th of June, if only the year is available.
- If the imputed start date is after the concomitant medication end date, further adjustment of the imputed start date is required. It will be imputed as the concomitant medication end date.
- No imputation if completely missing.

If the medication was taken prior to study start (TP1 Day 1) based on eCRF question, and the imputed start date is after first treatment date, further adjustment of the imputed start date is required. It will be imputed as the day prior to first dosing date.

If the medication was taken after study start (TP1 Day 1) based on eCRF question, and the imputed start date is prior to first dosing date, the imputed start date will be further adjusted to be the first study treatment dosing date. The partially missing medication end date will be imputed following the rule described at the beginning of this section to ensure it is on or after first dosing date, and after its start date.

- In case of a completely missing start date, the concomitant therapy will be considered as having started before the trial, unless the eCRF indicating that the medication was taken after study start.
- In case of a completely missing end date, the concomitant therapy will be considered as ongoing at the end of the trial, unless the eCRF indicating not ongoing.

5.1.8.4. Dates of Alcohol Consumptions

In case of partially missing start/end dates, the following imputation rules will be applied:

- the 15th of the month, if only the day is missing.
- the 30th of June, if only the year is available.
- If the imputed start date is after the end date, further adjustment of the imputed start date is required. It will be imputed as the end date.
- If end date is completely missing and marked as Ongoing then impute with baseline visit date. Otherwise, no imputation if completely missing.

5.1.9. Data Handling Rules

Those measurements collected from screening visit to the end of study will be handled according to the following rules summarized in [Table 5](#).

Table 5: Data Handling Rules for HBV Virology and Serology Assessments

HBV parameter	LLOQ	ULOQ	Imputed Values	
			If value < LLOQ	If value > ULOQ
HBsAg	0.05 IU/mL	249,750.00 IU/mL with dilution	0.025 IU/mL ^(a)	274,725.00 IU/mL ^(b) with dilution
HBeAg	0.11 IU/mL	7,000.00 IU/mL with dilution	0.055 IU/mL ^(a)	7,700.00 IU/mL ^(b) with dilution
HBcrAg*	3.0 log ₁₀ U/mL	9.0 log ₁₀ U/mL with dilution	2.7 log ₁₀ U/mL	9.9 log ₁₀ U/mL ^(b) with dilution
HBV DNA	20 IU/mL	170,000,000 IU/mL w/o dilution	If target detected: 15 IU/mL If target not detected: 5 IU/mL**	187,000,000 ^{(b)(c)} IU/mL w/o dilution
HBV RNA*	LLOQ = 2.939 log ₁₀ cp/mL (i.e. 869 cp/mL) LOD = 1.398 log ₁₀ cp/mL (i.e. 25 cp/mL)	NAP	If <LOD or target not detected then 1.114 log ₁₀ cp/mL (i.e. 13 cp/mL)	NAP
Anti-HBs	5 mIU/mL	10,000.0 mIU/mL	2.5 mIU/mL ^(a)	11,000.0 mIU/mL ^(b)

* As new assays become available different data handling rules may apply.

** For HBV DNA <LLOQ: Spaghetti plots showing absolute values, the imputed value will be 15 IU/mL for both target detected, and target not detected. All other tables, listings, and figures will be produced using 15 IU/mL as an imputed value if target is detected and 5 IU/mL if target is not detected.

Key: NAP=Not applicable

(a) LLOQ/2

(b) ULOQ+(ULOQ/10)

(c) If the original result > ULOQ, then take the re-test value (i.e. diluted result). If the diluted result is not available, use the imputed value indicated in this table

All other viral activity data with values <LLOQ which are not included in the data handling rules above will be imputed by the absolute value divided by 2.

5.1.10. Main Groups for Analysis

While most analyses will be focused on all subjects without separating by study intervention, some analysis will be performed in three different groups:

1. Group 1: Participants who received at least one tablet of JNJ-6379 during treatment period 2:
 - Treatment Period 1: JNJ-3989 + JNJ-6379 + NA
 - Treatment Period 2: JNJ-3989 + JNJ-6379 + NA + PegIFN- α 2a
2. Group 2: Participants who did not receive JNJ-6379 at treatment period 2:
 - Treatment Period 1:
 - JNJ-3989 + JNJ-6379 + NA
 - JNJ-3989 + NA
 - Treatment Period 2: JNJ-3989 + NA + PegIFN- α 2a

Some analysis will be performed separately by the study intervention of treatment period 1 and overall.

3. Group 3: all participants who were enrolled in the trial

Post-hoc analyses may be performed based on duration of exposure to JNJ-6379.

5.1.11. On-treatment and off-treatment periods

The on-treatment period begins with the first drug intake date and finishes with the maximum between:

- Last dose of NA + 2 days
- Last dose of PegIFN α 2a + 10 days,
- Last dose of JnJ-3989 + 28 days.

The off-treatment period stops if the NA re-treatment starts.

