5.4.1.1.16. Flares

The criteria based on blood markers/lab tests for each of the flare types are defined as below.

1. Virologic flare is defined as follows:

Virologic flare will be assessed only for those participants who are off-treatment and had HBV DNA $< \text{LLOQ}$ at the last observed point on all study treatments.

The start of a confirmed virologic flare is defined as the first date of two consecutive visits with HBV DNA >200 IU/mL. The end date of the same confirmed virologic flare is defined as the first date when HBV DNA value returns to ≤ 200 IU/mL or the date of NA treatment restart, whichever comes first. Each virologic flare will be categorized based on the confirmed (i.e. two consecutive values) peak HBV DNA above any of the three thresholds within the start and end date of that flare as follows: 20,000 IU/mL, 2,000 IU/mL and 200 IU/mL.

- 1 (Yes) = confirmed** HBV DNA $>$ peak threshold.
- 0 (No) = at least one off-treatment HBV DNA measurement available and not meeting the criteria of confirmed HBV DNA $>$ peak threshold.
- 2 (Not applicable) = no off-treatment HBV DNA quantitative measurements available.

2. Off-treatment Biochemical flare is defined as follows:

The start date of a confirmed off-treatment biochemical flare is defined as the first date of two consecutive visits with ALT and/or AST $\geq 3x$ ULN and $\geq 3x$ nadir (i.e. lowest value observed up to the start of the flare) while the participant does not receive any of the study interventions. The end date of the same off-treatment biochemical flare is defined as the first date when there is a 50% reduction from the peak ALT and/or AST level & $< 3x$ ULN.

- 1 (Yes) = confirmed** ALT and/or AST $\geq 3x$ ULN and $\geq 3x$ nadir (i.e. lowest value observed up to the start of flare)
- 0 (No) = otherwise

3. On-treatment Biochemical flare is defined as follows:

The start date of a confirmed on-treatment biochemical flare is defined as the first date of two consecutive visits with ALT and/or AST $\geq 3x$ ULN and $\geq 3x$ nadir (i.e. lowest value observed up to the start of the flare) while the participant receives any of the study interventions. The end date of the same on-treatment biochemical flare is defined as the first date when there is a 50% reduction from the peak ALT and/or AST level & $< 3x$ ULN, regardless of stopping the study interventions.

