- 1 (Yes) = confirmed** ALT and/or AST $\geq 3x$ ULN and $\geq 3x$ nadir (i.e. lowest value observed up to the start of flare)
- 0 (No) = otherwise

4. Clinical flare is defined as follows:

A clinical flare occurs either when a virologic flare and biochemical flare overlap in time or when a biochemical flare starts within 4 weeks following the end of a virologic flare. The start date of a clinical flare is defined as the minimum start date of the virologic flare and the biochemical flare. The end date of a clinical flare is defined as the maximum end date of the virologic flare and biochemical flare, i.e., the later date of HBV DNA returns to ≤ 200 IU/mL and 50% reduction from the peak ALT and/or AST level.

- 1 (Yes) = confirmed** HBV DNA $>$ peak threshold and confirmed** ALT and/or AST $\geq 3x$ ULN and confirmed** $\geq 3x$ nadir (i.e. lowest value during study participation).
- 0 (No) = otherwise

** Confirmed means that the criterion should be fulfilled at 2 or more consecutive time points or at the last observed time point.

The virologic and clinical flares will be assessed only off-treatment, while biochemical flares will be identified on-treatment and off-treatment. On-treatment virologic flares are described as virologic breakthrough in Section 5.4.1.1.15. On-treatment will be defined as the time period in which the participant receives any of the study interventions. Off-treatment will be defined as the period after stopping all study interventions (including NA).

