5.4.2.1.15. Flares

The incidence rate will be calculated and summarized for each type of on-treatment or off-treatment flares (virologic, biochemical and clinical) separately, as well as the overall incidence of participants experiencing at least one flare, regardless of type. Additionally, for each participant the total number of flares the participant experienced will be counted by type. Such counts will be used to summarize the distribution of the total number of flares by type.

For on-treatment biochemical flares, the incidence of flares causing treatment discontinuation will be summarized. Further, for off-treatment flares, the count and percentage of participants who experienced a flare followed by NA re-treatment will be summarized by flare type. Similarly, the incidence of flares followed by the achievement of HBsAg seroclearance (at any time) will be summarized by flare type.

Flares that are associated with signs of liver decompensation will be provided in a listing.

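### SAP 5.1.11 and 5.4.1.3.7 do not limit the last dose to the period before NA re-treatment; read literally, they erase the off-NA interval and give a negative time to flare

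*SAP*

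**What the plan says.** SAP 5.1.11 is where the SAP gives a dated rule for the on-treatment period: "The on-treatment period begins with the first drug intake date and finishes with the maximum between" three terms. These are "Last dose of NA + 2 days", the last PegIFN-α2a dose plus 10 days, and "Last dose of JnJ-3989 + 28 days". The section then closes with "The off-treatment period stops if the NA re-treatment starts". It does not say whether the last NA dose means the end of the initial course or the last NA dose in the study.

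SAP 5.4.1.3.7 measures time to first off-treatment flare as the flare date minus the date of last study intervention intake, again without reference to re-treatment. SAP 5.1 includes NA in study intervention.

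The endpoint definitions use a different basis:

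- SAP 5.4.1.1.15 (virologic breakthrough) takes on-treatment as the time in which the participant is receiving any study intervention, NA included.
- SAP 5.4.1.1.16 (flares) splits biochemical flares by whether the participant is or is not receiving study intervention. It defines off-treatment as the time after all interventions, NA included, have been stopped. It ends a virologic flare when HBV DNA returns to 200 IU/mL or below, "or the date of NA treatment restart, whichever comes first".
- SAP 5.4.2.1.15 plans that "for off-treatment flares, the count and percentage of participants who experienced a flare followed by NA re-treatment will be summarized by flare type".

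**The concern.** Under Protocol 6.6, a participant who meets the NA completion criteria at Week 24 stops NA at FU Week 2. Under Protocol 6.7.1 the same participant may restart NA later. The interval between stop and restart is where the safety of stopping NA is observed. Because 5.1.11 takes a maximum over last-dose dates, one NA dose after restart is enough to move the end of on-treatment past that interval. The time origin in 5.4.1.3.7 moves with it.

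The period label matters because breakthrough and virologic flare share the same HBV DNA threshold. Breakthrough is a confirmed on-treatment value above 200 IU/mL in someone who had been below the LLOQ. A virologic flare is a confirmed off-treatment value above 200 IU/mL in someone below the LLOQ at the last point on treatment. The completion criteria require HBV DNA below the LLOQ at Week 24, so participants who stop NA on those criteria meet the precondition for breakthrough. If a programmer took the 5.1.11 dates as the flag for these endpoints, an off-NA rebound could move from one secondary endpoint to another.

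**Working it through.** No figure in the plan depends on this rule, so there is none to reproduce. The Clopper-Pearson 90% intervals in SAP 3 do reproduce (25/50: 0.376 to 0.624; 10/20: 0.302 to 0.698), but they are not inputs here.

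**General argument.** Let J, P and L be the days of the last JNJ-3989, PegIFN-α2a and NA doses in the study, S the last NA dose before re-treatment, F the start of the flare and R the NA restart, with S < F < R ≤ L.

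- Literal end of on-treatment: E = max(L + 2, P + 10, J + 28) ≥ R + 2. E lies after R, so no day is both after E and before R, and off-treatment time before restart is 0.
- Literal time to flare: F - L. Since F < R ≤ L, this is always negative.

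Neither result depends on how long re-treatment lasts.

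**Illustrative record.** Scheduled days come from the Schedule of Activities and SAP Table 4. The timing of flare, restart and last NA dose is assumed.

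| Input | Day | Source |
|---|---|---|
| Last JNJ-3989 dose, Week 20 (J) | 141 | Schedule |
| Last of 12 weekly PegIFN-α2a doses from Day 85 (P) | 85 + 7 × 11 = 162 | Schedule |
| Week 24 visit, taken as FU Day 1 | 169 | Schedule; assumption |
| First NA stop, FU Day 15 (S) | 168 + 15 = 183 | Protocol 6.6 |
| Flare start, FU Day 85 (F) | 168 + 85 = 253 | assumption |
| NA restart, FU Day 113 (R) | 168 + 113 = 281 | assumption |
| Last NA dose, FU Day 337 (L) | 168 + 337 = 505 | assumption |

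*Literal reading.* On-treatment ends at max(505 + 2, 162 + 10, 141 + 28) = max(507, 172, 169) = Day 507. Off-treatment time before Day 281 is 0 days, and the Day 253 flare lies inside the on-treatment period. Time to flare is 253 - 505 = -252 days.

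*Reading the last NA dose as the last before re-treatment.* On-treatment ends at max(183 + 2, 172, 169) = Day 185. Off-treatment runs from Day 186 to Day 280, which is 280 - 185 = 95 days. The Day 253 flare is off-treatment, and time to flare is 253 - 183 = 70 days.

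*Sensitivity.* If FU Day 1 is Day 170, every follow-up day moves by one. The results 0, 95, -252 and 70 do not change.

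**Comparison with the endpoint definitions.** By actual receipt (5.4.1.1.15 and 5.4.1.1.16), the participant takes nothing from Day 184 to Day 280, which is 280 - 183 = 97 days. The Day 253 event is therefore off-treatment whatever 5.1.11 says. The 2-day difference from 95 is the NA lag in 5.1.11.

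**The case against.** The strongest reply is that the SAP already rules out the literal reading. The closing sentence of 5.1.11 ends off-treatment at re-treatment, which presupposes an off-treatment period before it. The SAP treats NA re-treatment as a separate event elsewhere, in functional cure, partial cure and the censoring rules. The breakthrough and flare sections do not refer to 5.1.11. They use actual receipt, and 5.4.1.1.16 provides for a virologic flare that is ended by NA restart.

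Most of this stands. The intent is clear, and a careful programmer would probably follow it. It does not repair the two rules, though. The closing sentence of 5.1.11 says when off-treatment stops, not when it starts, and the start still hangs on an unqualified maximum. Nothing in 5.4.1.3.7 limits the last intake to the period before re-treatment. A rule that yields a negative event time cannot be programmed as written.

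A reader might infer more: that re-treated participants have no off-treatment period at all, that the flare leading to re-treatment cannot count as off-treatment or turns into an on-treatment event, and that the planned summary of flares followed by re-treatment is zero by construction. The documents do not support this. An off-NA ALT flare does not occur while study intervention is being received, so it fails the on-treatment definition in 5.4.1.1.16. An off-NA rebound likewise fails the on-treatment condition for breakthrough in 5.4.1.1.15. Both count as off-treatment under the definitions written for them, and the 5.4.2.1.15 summary follows from those definitions.

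**Conclusion.** The point holds as a drafting fault in two rules. For every participant who stops NA, flares and then restarts, 5.1.11 read literally labels the whole off-NA interval on-treatment, against its own next sentence and against 5.4.1.1.15 and 5.4.1.1.16. For the same participants, 5.4.1.3.7 read literally gives a negative time to the flare that preceded re-treatment. In the illustrative record the sizes are 0 against 95 off-treatment days, and -252 against 70 days to flare.

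The signs are general; the magnitudes rest on the assumed visit days. The documents do not say how many participants were re-treated. Enrolment is about 50 and only a subset stops NA, so the number affected may be small, but so is the denominator for these summaries. Flare and breakthrough counts are at risk only if someone derives them from the 5.1.11 dates. The SAP does not say which definition governs, so that remains possible. The primary endpoint (HBsAg reduction at Week 24) and the sample-size precision figures are unaffected.

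**What to change.** 1. In SAP 5.1.11, change the NA term to: last dose of NA before any NA re-treatment + 2 days. Add that the off-treatment period runs from the end of the initial on-treatment period to the start of NA re-treatment.
2. In SAP 5.4.1.3.7, change the time origin for off-treatment flares to: last study intervention intake before any NA re-treatment.
3. State that the definitions in 5.4.1.1.15 and 5.4.1.1.16 govern the classification of breakthrough and flares.

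The 2-, 10- and 28-day lags of 5.1.11 should not be carried into 5.4.1.1.15 and 5.4.1.1.16 in the name of consistency. That would change when an event counts as off-treatment, notably after early discontinuation, and would be a new analysis choice rather than a correction.

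The cost is a few sentences in the SAP and a check of two derived dates: the end of on-treatment and the origin for time to off-treatment flare. No new data are needed.

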5.2. Participant Dispositions

All the summaries will be done on the FAS analysis set. The IFN-FAS and modified FAS/IFN-FAS analysis sets will be used if there is a difference of at least 2 participants between analysis sets.

Screened participants and reason for screen failures will be summarized overall.

The number of participants in the following disposition categories will be summarized by analysis phase.

- Participants who received any study intervention (JNJ-3989, JNJ-6379, PegIFN- α 2a or NA)
- Participants in each study analysis phase
- Participants who completed the study

- Participants who discontinued study interventions
 - Reasons for discontinuation of study interventions
- Participants who terminated study prematurely
 - Reasons for termination of study

A listing of participants will be provided for the following categories

- Participants who discontinued study interventions
- Participants who terminated study prematurely

5.3. Primary Efficacy Endpoint

5.3.1. Definition

The primary endpoint is the proportion of participants with a reduction of at least 2 log₁₀ IU/mL in HBsAg levels from baseline to Week 24.

5.3.2. Analysis Methods

The main analysis of the primary endpoint will be conducted using the FAS. The IFN-FAS and modified FAS/IFN-FAS analysis sets will be used if there is a difference of at least 2 participants between analysis sets.

Some analysis will be performed by group, as defined in Section 5.1.10 above.

The count and proportion of participants with a reduction of at least 2 log₁₀ IU/mL in HBsAg levels from baseline to Week 24 and the associated 90% CI using the Clopper-Pearson method will be calculated.

5.3.2.1. Missing Data Handling Rule

The missing as non-responder is the primary rule to handle missing data. Two sensitivity analyses will be conducted using the observed case data and LOCF approach, respectively.

5.3.2.1.1. Missing as Non-Responder

Participants who do not have HBsAg data in the analysis window of Week 24 will be defined as non-responders.

5.3.2.1.2. Observed Case Analysis

Only participants who have HBsAg data at Week 24 will be used for the analysis.

5.3.2.1.3. Last Observation Carried Forward (LOCF)

If the HBsAg value at Week 24 is missing, the non-missing value closest to Week 24 within the window of 4 weeks prior/after Week 24 visit will be used. If 2 non-missing laboratory values are equidistant, the later observation will be preferred. Participants who do not have data within the analysis window of ±4 weeks around the Week 24 assessment will be defined as non-responders.

5.4. Secondary Efficacy Endpoints

See Section 1.1 for a list of the secondary endpoints. All secondary endpoints will be analyzed using observed case data. Additional analyses with specific imputation methods for missing data are added for selected endpoints.

5.4.1. Definitions

5.4.1.1. Binary Endpoints

5.4.1.1.1. NA Treatment Completion Criteria at Week 24 and During FU

NA treatment completion criteria are defined based on laboratory results at Week 24 as follows:

- HBsAg <10 IU/mL, and
- HBeAg-negative, and
- HBV DNA <LLOQ, and
- ALT <3x ULN

The NA completion criteria will be assessed based on clinical laboratory tests and summarized at Week 24 (EOSI) and during FU phase.

5.4.1.1.2. NA Re-Treatment Criteria During FU

Participants who actually re-started NA treatment during the follow-up phase will be identified based on the 'Study Drug Administration for NA' CRF page.

Participants who meet the NA re-treatment criteria will be identified on the CRF page of 'NA Re-treatment Criteria Assessment'.

5.4.1.1.3. HBsAg Cut-offs

The cut-offs for HBsAg level are as follow:

- <1000 IU/mL
- <100 IU/mL
- <10 IU/mL
- <1 IU/mL
- <LLOQ (0.05 IU/mL)

The cut-offs for HBsAg change from baseline and RT are as follow:

- decrease by $\geq 0.3 \log_{10}$ IU/mL
- decrease by $\geq 0.5 \log_{10}$ IU/mL
- decrease by $\geq 1 \log_{10}$ IU/mL
- decrease by $\geq 2 \log_{10}$ IU/mL

- decrease by $\geq 3 \log_{10}$ IU/mL
- decrease by $\geq 4 \log_{10}$ IU/mL

5.4.1.1.4. HBsAg Seroclearance

Seroclearance of HBsAg is defined as a (quantitative) HBsAg level <LLOQ (see [Table 5](#)). HBsAg seroclearance can be observed prior to the time point assessed but must be observed at the given week of interest.

5.4.1.1.4.1. On Treatment

HBsAg seroclearance will be evaluated over time during the study intervention phase.

5.4.1.1.4.2. Off Treatment

HBsAg seroclearance will be evaluated over time at each of the FU timepoints separately, with emphasis at 12, 24, 36 and 48 weeks after stopping all study interventions at the end of treatment period 2 and without restarting NA treatment.

HBsAg seroclearance will be also evaluated when assessed at 12, 24, 36 and 48 weeks after stopping all study interventions (regardless when intervention was stopped) and without restarting NA treatment.

For the analyses of seroclearance at the time points mentioned above, participants with HBsAg seroclearance at the respective time points (and without restarting NA treatment during the interval between the time of stopping the study intervention up to the analysis time point (FU Week 12, 24, 36 and 48)) will be considered as having achieved this endpoint.

